#### 3. Does the study involve a placebo? Yes

##### ► IF YES, provide a justification for the use of a placebo

LH secretory characteristics can be influenced by various factors such as time of day, stress, etc. Thus, defining LH secretory characteristics in the absence of progesterone is important for valid inference regarding the effects of progesterone.

## Human Participants

**Ages:** 18-35  
**Sex:** Female  
**Race:** All Races

**Subjects-** see below

**INSTRUCTIONS:** For question 1-4 below insert an exact #. Ranges or OPEN is not allowed. This # should be the maximum # you expect to need to enroll (i.e. sign consent) If you are only collecting specimens the number of participants should equate to the # of specimens you need. If you are collecting only data from a chart review the number should designate the number of subjects whose medical records you plan to review. Age/ Sex/Race criteria should designate the demographics of participants from whom you will obtain the specimen/data.

**1. Provide target # of subjects (at all sites) needed to complete protocol.**

Twelve ovulatory subjects and twelve women with PCOS are needed to complete the protocol. (Update at time of 5-year renewal April 2017: we have completed study of all required controls, and we are nearing completion of study in women with PCOS.)

**2. Describe expected rate of screen failure/ dropouts/withdrawals from all sites.**

We anticipated that approximately one-third would fail screening, and that one-third would either dropout or withdraw from the study. Since the study inception, 81 subjects have been enrolled in the study. To date, 59 of those subjects enrolled have either dropped out or been withdrawn from the study, ~ 73%.

**3. How many subjects will be enrolled at all sites?**

N/A – this is a single site study

**4. How many subjects will sign a consent form under this UVa protocol?**

90 subjects will sign a consent form under this protocol. (*Notably, we will stop recruiting when we have obtained complete and interpretable data for 12 women with PCOS and 12 controls*). (Update at time of 5-year renewal April 2017: we have completed study of all required controls, and we are nearing completion of study in women with PCOS.)

**5. Provide an estimated time line for the study.**

We anticipate 100% enrollment in two years and 50% completion of data analysis in five years. (Update at time of 5-year renewal April 2017: We anticipate completion of the study no later than 2019.)

## Inclusion/Exclusion Criteria

### 1. List the criteria for inclusion

#### Criteria for inclusion:

- Subjects will be healthy women in two groups: (1) women with regular menstrual cycles and no evidence of hyperandrogenism, and (2) women with PCOS (defined as clinical/biochemical evidence of hyperandrogenism plus oligomenorrhea, but with no evidence for other endocrinopathies).
- Subjects will be 18-35 years old; we use a cutoff age of 35 years because early menopause at this age is very rare, and the risk of DVT with estrogen use may increase beyond this age.
- Subjects will be willing to strictly avoid pregnancy (using non-hormonal methods) during the time of study and must be willing and able to provide informed consent.

### 2. List the criteria for exclusion

#### Criteria for exclusion:

- We will exclude women with a history of any disorders that may potentially be complicated by hormonal treatment, such as DVT and breast, ovarian, or endometrial cancer.
- We will exclude women with any other cancer diagnosis and/or treatment (with the exception of basal cell or squamous skin carcinoma) unless they have remained clinically disease free (based on appropriate surveillance) for five years.
- Women with anemia (hematocrit  $\leq$  36% and/or a hemoglobin level  $<$ 12 g/dl) will be treated with iron for a maximum of 2 sequential months before the 1st admission and/or before the 2nd admission. If they remain anemic after 2 sequential months of ferrous gluconate (325 mg bid), they will then be excluded from further participation in the study.
- Women with a history of any disorders that may potentially be complicated by long-term iron supplementation, such as hemochromatosis and polycythemia vera, will be excluded.
- Women with a significant history of cardiac or pulmonary dysfunction (e.g., known or suspected congestive heart failure; known or suspected coronary atherosclerosis; asthma requiring systemic intermittent corticosteroids; etc.) will be excluded.
- Women with liver enzymes, alkaline phosphatase, or bilirubin  $>$  1.5 times upper limit of normal (confirmed on repeat) will be excluded, with the exception that mild bilirubin elevations will be accepted in the setting of known Gilbert's syndrome.
- Abnormal sodium or potassium concentrations (confirmed on repeat); bicarbonate concentrations  $<$ 20 or  $>$ 30 (confirmed on repeat)
- Women with abnormal renal function (i.e., serum creatinine  $>$  1.4) will be excluded (confirmed on repeat)
- Pregnant and breast-feeding women will be excluded.
- A history of allergy to progesterone or estradiol will constitute grounds for exclusion.
- Women with a BMI greater or equal to 40 kg/m^2.
- Virilization
- A total testosterone  $>$  150 ng/dl in women with PCOS (which suggests the possibility of a virilizing neoplasm) (confirmed on repeat)
- Elevated DHEAS (mild elevations may be seen in PCOS, and elevations  $<$  1.5 times the upper limit of normal will be accepted in PCOS) (confirmed on repeat)
- Follicular 17-hydroxyprogesterone  $>$  300 ng/dl, which suggests the possibility of congenital adrenal hyperplasia (if elevated during the luteal phase and there is a concern about the possibility of congenital adrenal hyperplasia, the 17-hydroxyprogesterone may be collected during the follicular phase, or  $>$ 60 if oligomenorrhic). *NOTE:* If a 17-hydroxyprogesterone  $>$  300 ng/dl is confirmed on such repeat testing, an ACTH stimulated 17-hydroxyprogesterone  $<$  1000 ng/dl will be required for study participation.
- A previous diagnosis of diabetes, a fasting glucose  $\geq$  126 mg/dl, or a hemoglobin A1c  $>$  6.5%

- Abnormal TSH (subjects with adequately treated hypothyroidism, reflected by normal TSH values, will not be excluded; or, for a new diagnosis of hypothyroidism, further study will at the least be delayed pending appropriate treatment) (confirmed on repeat)
- Abnormal prolactin (mild elevations may be seen in PCOS, and elevations < 1.5 times the upper limit of normal will be accepted in this group) (confirmed on repeat)
  - Evidence of Cushing’s syndrome by history or physical exam

Due to the amount of blood being drawn in the study, subjects with body weight < 110 lbs. will be excluded from the study

**3. List any restrictions on use of other drugs or treatments.**

Being a study of reproductive hormonal effects on the hypothalamic-pituitary unit, subjects must not take hormonal medications (e.g., oral contraceptives) or other medications known to affect the reproductive axis for 90 days prior to the study and during the study.

**Statistical Considerations**

**1. Is stratification/randomization involved? Yes**

**► IF YES, describe the stratification/ randomization scheme.**

The subjects will be randomized to receive either progesterone or placebo during the first CRU admission. This randomization will be generated by the CRU biostatistician using the PROC PLAN procedure of SAS version 9.3 (SAS Institute Inc., Cary NC).

**► IF YES, who will generate the randomization scheme?**

UVa Statistician. [name]

**2. What are the statistical considerations for the protocol?**

This is a randomized, placebo-controlled, cross-over study.

**3. Provide a justification for the sample size used in this protocol.**

Sample size/statistical power: The primary endpoint will be the change in LH pulse frequency (over 10 h) attributable to P. The null hypothesis is that 10-h (1000-2000 h) LH frequency after P administration will be the same as 10-h (1000-2000 h) LH frequency after placebo administration. Estimates of within-subject variability utilized in the calculation (column 2 of table below) were based on our preliminary data. Assuming that 12 women in both groups complete both CRU admissions (placebo admit, P admit), we list in column 3 (table) the estimates for the minimum detectable absolute difference between the mean change in 10-h LH pulse frequency that would provide ≥ 80% statistical power.

Endpoint	Within-subject standard deviation	Minimum detectable P effect on LH frequency
Change in LH pulse-interval (min)	20.6	16.7
Change in # of LH pulses / 10-h	1.24	1.0

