**4. What is your plan for primary variable analysis?**

Data analysis plan: 10-h LH pulse frequency will be analyzed using hierarchical mixed-effects ANOVA models. Each ANOVA model will be structured to examine whether exogenous P affects LH frequency. In the ANOVA model, “subject” will be a blocking factor, while the treatment condition (placebo, P) will be modeled as highest within-subject level factor, and the measurement assessment time (10-h baseline sampling period, 10-h post-treatment sampling period) will be modeled as the lowest within-subject level factor. Treatment by measurement assessment time interaction will also be modeled. We will use linear-contrasts of the ANOVA least-squared means to test our a priori research hypothesis. Specifically, we will test whether the change in mean LH frequency from the baseline state to the post-

treatment state differed depending on whether placebo or P was administered at 0600 h. 95% confidence interval construction (for the estimation of the true magnitude of P effect) will be based on the t-distribution. Traditional residual diagnostics will be conducted to evaluate model goodness of fit. If LH frequency data fail to adhere to equal variance and normality assumptions of linear mixed-effects models, the data will be analyzed using a generalized linear mixed-effect-model in a similar format, with the exception that LH pulses as will be modeled as counts utilizing either a Poisson or a Negative-Binomial distribution. Similar statistical procedures will be used to compare the effects of P in controls vs. PCOS: in the ANOVA model, PCOS status (no, yes) will be a between-subject factor, while the treatment (placebo, progesterone) will be a within-subject factor.

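### The detectable progesterone effects in the sample size table rest on a normal approximation; under the planned t-based contrast they have about 76–78% power, not at least 80%, and the contrast behind the tabulated SD is not stated

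*Combined protocol and SAP*

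**What the plan says.** Statistical Considerations, item 3 (sample size), sets an equality null: "LH frequency after P administration will be the same as 10-h (1000-2000 h) LH frequency after placebo administration". Its planning condition reads "Assuming that 12 women in both groups complete both CRU admissions (placebo admit, P admit". The table then gives a "Within-subject standard deviation" of 20.6 min for the change in pulse interval and 1.24 for the change in pulse count. Against these stand minimum detectable progesterone effects of 16.7 min and 1.0 pulse, described as "the minimum detectable absolute difference between the mean change in 10-h LH pulse frequency that would provide ≥ 80% statistical power". Alpha, sidedness, formula and degrees of freedom are not given.

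Item 4 (primary variable analysis) describes a hierarchical mixed-effects ANOVA. Treatment is the upper within-subject factor, and assessment time (baseline or post-treatment) "will be modeled as the lowest within-subject level factor. Treatment by measurement assessment time interaction will also be modeled". The test asks whether the change from the baseline to the post-"treatment state differed depending on whether placebo or P was administered at 0600 h". On inference it says "95% confidence interval construction (for the estimation of the true magnitude of P effect) will be based on the t-distribution". For the comparison of groups, "PCOS status (no, yes) will be a between-subject factor".

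Under Hypothesis to be Tested, hypothesis 1 concerns normally cycling women only; hypothesis 2 compares women with PCOS against them.

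**The concern.** With only 12 women per group, the gap between normal and t critical values is not negligible. If the detectable effects were computed with normal quantiles while the analysis uses t quantiles on a few tens of degrees of freedom, the promised 80% is not delivered at the printed effects.

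The second issue may be larger. A within-subject SD of a change can mean the SD of each woman's progesterone-minus-placebo difference in change, or the SD of the change within a single admission. The two differ by a factor of √2 in the standard error for the same women. The answer decides whether the table describes hypothesis 1 in 12 women or a progesterone effect averaged over all 24. A reader who has to interpret a non-significant result in the controls needs to know which.

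**Working it through.** **Inputs.** From item 3: SDs 20.6 min and 1.24 pulses; effects 16.7 min and 1.0 pulse; 12 women per group, each with two admissions; power at least 80%. From item 4: the treatment-by-time contrast and t-based inference. Assumed: two-sided alpha 0.05.

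**1. Reproducing the table.** Detectable effect = (z₀.₉₇₅ + z₀.₈₀) × SE, with SE = SD/√12.

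- Interval: (1.960 + 0.842) × 20.6/√12 = 2.802 × 5.947 = 16.66, printed 16.7.
- Count: 2.802 × 1.24/√12 = 2.802 × 0.358 = 1.003, printed 1.0.

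One-sided 5% normal quantiles give 14.8 min and 0.89 pulses, which do not match. The table is therefore a two-sided 5% normal approximation.

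**2. Degrees of freedom for the planned contrast.**

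- 12 women × 2 admissions × 2 periods = 48 observations: 1 mean + 11 subject + 1 treatment + 11 treatment error + 1 time + 1 interaction + 22 residual.
- Both groups, 96 observations: 1 mean + 1 group + 22 subject + 1 treatment + 1 group-by-treatment + 22 error + 4 time terms + 44 residual.
- If the admission-level error is not separated, 22 + 44 = 66.
- Analysing the 12 per-woman differences directly gives 11.

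**3. Power at the printed effects.** The noncentrality is 16.7/5.947 = 2.808 (interval) and 1.0/0.358 = 2.794 (count). Power is the probability that a noncentral t exceeds the two-sided 5% critical value.

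| df | Power at 16.7 min | Power at 1.0 pulse | 80% detectable, min | 80% detectable, pulses |
|---|---|---|---|---|
| 11 | 0.725 | 0.7205 | 18.31 | 1.102 |
| 22 | 0.7655 | 0.761 | 17.43 | 1.049 |
| 44 | 0.784 | 0.780 | 17.04 | 1.025 |
| 66 | 0.790 | 0.786 | 16.91 | 1.018 |

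Rounding does not rescue the interval row: at 16.75 min, the top of the band that rounds to 16.7 or 16.8, power is 76.8% on 22 df, 78.7% on 44 and 79.3% on 66. In the count row, the t-based 1.049 and 1.025 still round to the printed 1.0, so the discrepancy is visible only in the interval row.

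**4. Which contrast the SD describes.** SE = SD/√12 arises in two ways:

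- (i) SD of the per-woman progesterone-minus-placebo difference in change, with n = 12.
- (ii) SD of the change within one admission, with 24 women pooled, because SD × √(2/24) = SD/√12.

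Under (ii), the pooled progesterone effect has the power shown for 22 to 66 df, about 76–79%. A test in the 12 controls alone has SE = SD × √(2/12), that is 8.41 min and 0.506 pulses. At the printed effects:

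| df | Power, interval | Power, count | 80% detectable |
|---|---|---|---|
| 11 | 0.441 | 0.438 | 25.9 min / 1.56 pulses |
| 22 | 0.476 | 0.472 | 24.7 min / 1.48 pulses |

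Estimating the controls' effect in the two-group model on 44 df raises this only to about 49%.

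**The case against.** The shortfall is small, and the planning SDs are themselves estimates from preliminary data. For the interval, an SD 2% smaller brings power to 80.0% on 44 df, and one 5% smaller brings it to 80.6% on 22 df. Normal quantiles are a common planning shortcut, and item 4 does not name a degrees-of-freedom method, so 22 is not established as the plan's value. Hypothesis 1 is directional: a one-sided 5% t-test would have 83–87% power at the printed effects on 11 to 66 df. The controls-only figure depends on a reading of the SD that the text does not confirm. The 22 df value under reading (i) also assumes no subject-by-time variance. Finally, the controls are complete and recruitment of women with PCOS is nearly so (Human Participants, items 1 and 4), and the planned confidence interval will show the precision achieved.

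Much of this stands as a limit on size: the miss is modest, and the low controls-only power is conditional. It does not restore the claim. One-sided normal quantiles do not reproduce the table, and both the equality null and the wording of the test point to two sides. No two-sided t reading among those examined reaches 80%. Subject-by-time variance would inflate the 22 df residual and lower power further, which is why the 11 df value is given as the conservative one.

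**Conclusion.** The concern holds. Assuming two-sided 0.05 and SE = SD/√12, power at the printed effects is about 3 to 4 points below 80% on 22 df, about 2 points below on 44 df, and 7 to 8 points below on 11 df. The corresponding detectable effects rise by about 2% on 44 df (17.04/16.66) and 5% on 22 df (17.43/16.66).

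The unstated contrast matters more than the choice of quantile. If the SD is per admission, the table speaks only for the pooled effect, and hypothesis 1 in the controls has less than 50% power at the printed effects. The documents do not settle which reading is right. This should be corrected, but it does not call the design or the analysis into question.

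**What to change.** Keep the sample size, model and test. In the sample size item:

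1. State alpha, sidedness, error degrees of freedom, and the contrast that the tabulated SD describes.
2. If it is the SD of the per-woman progesterone-minus-placebo difference in change, restate the effects as 17.4 min and 1.05 pulses (22 df), with 18.3 min and 1.10 pulses (11 df) as the conservative values. At exactly 17.4 min, power is 79.9%; print 17.5 (80.3%) if at least 80% is to hold strictly. Alternatively, keep 16.7 min and 1.0 pulse and state power of about 76%. Give pulses to two decimals.
3. If it is a per-admission SD with 24 women pooled, say that the table describes the pooled effect (power about 76–79%). Give hypothesis 1 separately: 24.7 min and 1.48 pulses (22 df), or 25.9 min and 1.56 pulses (11 df).

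As an optional addition, not a correction, give a detectable difference for hypothesis 2. Under reading (i), SE = SD × √(2/12) gives 24.1 min and 1.45 pulses (44 df) or 24.7 and 1.48 (22 df). Under reading (ii), SE = SD × √(4/12) gives 34.1 and 2.05, or 34.9 and 2.10.

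The cost is a change to wording and one table, with no extra participants.

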**4. What is your plan for primary variable analysis?**

Data analysis plan: 10-h LH pulse frequency will be analyzed using hierarchical mixed-effects ANOVA models. Each ANOVA model will be structured to examine whether exogenous P affects LH frequency. In the ANOVA model, “subject” will be a blocking factor, while the treatment condition (placebo, P) will be modeled as highest within-subject level factor, and the measurement assessment time (10-h baseline sampling period, 10-h post-treatment sampling period) will be modeled as the lowest within-subject level factor. Treatment by measurement assessment time interaction will also be modeled. We will use linear-contrasts of the ANOVA least-squared means to test our a priori research hypothesis. Specifically, we will test whether the change in mean LH frequency from the baseline state to the post-

treatment state differed depending on whether placebo or P was administered at 0600 h. 95% confidence interval construction (for the estimation of the true magnitude of P effect) will be based on the t-distribution. Traditional residual diagnostics will be conducted to evaluate model goodness of fit. If LH frequency data fail to adhere to equal variance and normality assumptions of linear mixed-effects models, the data will be analyzed using a generalized linear mixed-effect-model in a similar format, with the exception that LH pulses as will be modeled as counts utilizing either a Poisson or a Negative-Binomial distribution. Similar statistical procedures will be used to compare the effects of P in controls vs. PCOS: in the ANOVA model, PCOS status (no, yes) will be a between-subject factor, while the treatment (placebo, progesterone) will be a within-subject factor.

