Nocturnal, sleep-related slowing of LH pulse frequency during the early follicular phase is well described. Our data (above) and several studies by Loucks and colleagues (53-55) suggest that late follicular LH pulse frequency also slows by 20-30% during sleep. Nocturnal slowing of LH frequency in the early follicular phase (and presumably in the late follicular phase) appears to be specifically related to sleep and is likely driven by higher CNS systems.

These nocturnal changes in LH pulse frequency are interesting in light of what is observed during puberty. In early pubertal girls (and boys), nocturnal LH frequency *increases* compared to daytime LH frequency. It is generally believed that the overnight increase of LH pulsatility during puberty is driven by higher CNS systems.

Of particular interest, our preliminary data in peripubertal girls suggests that nocturnal LH frequencies in early pubertal girls, late pubertal girls, and the 8 adult women studied under JCM016 are very similar, while late evening LH frequencies (i.e., from 1900-2300 h – a surrogate for daytime frequency) are varied (Figure 2). These data are consistent with the notion that higher CNS systems may in large part determine nocturnal GnRH pulse frequency during puberty and in adults. Accordingly, sleep-associated (and presumably CNS-driven) LH frequency may be similar in pubertal girls and adult women, with daytime frequencies being controlled by other factors.

In addition, two of the aforementioned studies by Loucks and colleagues reported that dietary restriction slows daytime—but not nighttime—LH pulse frequency in the late follicular phase (53, 55). This suggests that daytime and nighttime LH frequency may be differentially affected by experimental maneuvers.

On the basis of the above observations, we have considered the possibility that *daytime* (or non-sleep-associated) LH frequency is acutely responsive to changes in P concentrations in women, even though nighttime frequency is not. This would be consistent with the notion that CNS control of *nocturnal* LH frequency may override hormonal control, at least in the short-term. We would like to test this hypothesis by using a protocol identical to the earlier JCM016 protocol except that the timing of the sampling and P (and PBO) administration is altered by exactly 12 hours (e.g., P and PBO are administered at 0600 h instead of 1800 h).

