### Hypothesis to be Tested

We propose two primary hypotheses: (1) administration of progesterone (at 0600 h) to normally cycling adult women during the follicular phase will result in a demonstrable suppression of daytime LH (and by inference GnRH) pulse frequency within 12 hours; (2) administration of progesterone (at 0600 h) to women with PCOS (during the follicular phase) will result in less suppression of daytime LH pulse frequency than in ovulatory women without PCOS. We will also assess the acute effects of progesterone on mean LH, LH pulse amplitude, and mean FSH. A secondary hypothesis is that LH augmentation after progesterone administration will be less in PCOS compared to normal controls.

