#### **5. What is your plan for secondary variable analysis?**

Secondary outcome variables (30-min measurements of P; 2-h measurements of P, FSH, E, T; LH pulse amplitude) will be analyzed via hierarchical mixed-effect ANOVA models (models/procedures identical to those above).

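### The crossover models name no admission-order (period) term: an order effect on the night-to-day change would bias the progesterone estimate at an unequal sequence split and stay in the error at an equal one

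*Combined protocol and SAP*

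**What the plan says.** All references are to the combined protocol and SAP.

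- **Randomisation** (Statistical Considerations, item 1): "The subjects will be randomized to receive either progesterone or placebo during the first CRU admission". The list comes from PROC PLAN. No ratio, block size or stratification by PCOS status is given.
- **Primary model** (item 4): subject is a blocking factor, "the treatment condition (placebo, P) will be modeled as highest within-subject level factor", and assessment time (10-h baseline or 10-h post-treatment window) is the lowest level, with treatment by time. The word period in this item means a sampling window, not a crossover period. The count fallback keeps a similar format.
- **Hypothesis 2** (item 4): "Similar statistical procedures will be used to compare the effects of P in controls vs. PCOS", with PCOS status between women and treatment within.
- **Secondary outcomes** (item 5): "models/procedures identical to those above".
- **Sample size** (item 3): the null is that 10-h "LH frequency after P administration will be the same as 10-h (1000-2000 h) LH frequency after placebo administration". This concerns the post-treatment window alone, whereas item 4 tests the change from baseline.

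No section names admission order, period or sequence as a model term.

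**The concern.** Order is the factor that the trial randomises, yet the models do not contain it. A shift that moves both windows of an admission equally cancels from the change contrast in item 4. An order effect on the change itself does not.

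Sleep is one possible route. The baseline window (2000-0600 h) contains the sleep period and the post-treatment window (1000-2000 h) is daytime. The Background says that "late follicular LH pulse frequency also slows by 20-30% during sleep". If women sleep differently on their first study night, only the baseline would move. This is a possibility, not a finding: no section reports a first-night effect, and the link between late-follicular slowing and sleep is itself only presumed ("and presumably in the late follicular phase) appears to be specifically related to sleep"). On the post-treatment-only null of item 3 a baseline-only shift would not enter, but a whole-admission shift would, and no order term is stated there either.

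Equal sequences among the women analysed are not assured. Recruitment stops on complete and interpretable data (Human Participants, item 4). Of 81 women enrolled, 59 had left (item 2), with timing relative to randomisation not given. An admission may also be repeated (Additional Note in Biomedical Research, item 1). Even a blocked list need not give 6:6 among 12 completers.

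**Working it through.** **Plan's own figure.** Item 3 tabulates SD 1.24 and 20.6 with detectable effects of 1.0 pulse and 16.7 min. With 12 women and a two-sided 5% level (assumed), (1.96 + 0.84) × 1.24/√12 = 1.00 and 2.80 × 20.6/√12 = 16.7. Both reproduce if 1.24 is the SD of the within-woman difference (reading A). They also reproduce if 1.24 is a per-admission SD and both groups are pooled: 2.80 × 1.24 × √2/√24 = 1.00 (reading B, SD of difference 1.24 × √2 = 1.75). Item 3 labels the column as a within-subject SD, so the text does not settle this. Power below is from the t distribution, which is why reading A starts at 72% (11 df) and not 80%.

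**Model.** Let d be the change on progesterone minus the change on placebo, τ the progesterone effect and π the order effect on the change (later minus first admission). Then E(d) = τ + π for placebo-first women (nA) and τ − π for progesterone-first women (nB).

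- Without period: E(mean d) = τ + π(nA − nB)/12.
- With period: the average of the two sequence means, which is unbiased, with SE = (SD/2)√(1/nA + 1/nB) on 10 df.
- At 6:6 without period: no bias, but the expected variance of d is SD² + π² × 12/11.

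**Size of π.** Not in the documents; 0.25 to 0.5 pulse per 10 h is assumed. For scale, one pulse per 60-90 min (Background) over 8 h of sleep, slowed by 20-30%, loses 480/90 × 0.20 = 1.07 to 480/60 × 0.30 = 2.4 pulses. The range is therefore 0.25/2.4 = 10% to 0.5/1.07 = 47% of that slowing.

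**Hypothesis 1, reading A, true effect 1.0, π = 0.25 / 0.5**

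| Split | Bias, no period | Power, no period | Power, period fitted |
|---|---|---|---|
| 6:6 | 0 | 71% / 66% | 71% |
| 8:4, bias adds | 0.08 / 0.17 | 77% / 80% | 66% |
| 8:4, bias subtracts | 0.08 / 0.17 | 63% / 50% | 66% |

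At 7:5 the bias is 0.25/6 = 0.04 and 0.5/6 = 0.08 pulse. Without period, type I error is 4.6% / 3.6% at 6:6 (conservative) and 5.1% / 5.5% at 8:4.

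**Chance of imbalance in a group of 12.** 8:4 or worse: 39% under simple allocation, 22% if 12:12 overall without stratification. 9:3 or worse: 15% or 4%. Both schemes are assumptions.

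**Averaged over allocation.** The bias is zero. Type I error without period is 5.0% / 5.1% (simple) or 4.8% / 4.3% (12:12 overall).

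**Hypothesis 2, reading A.** The bias is π times the difference between the two groups' imbalances. At 8:4 against 4:8 that is π × (4/12 + 4/12) = 0.17 / 0.33 pulse, with type I error 6% / 7%. A difference that large or larger has a 15% (simple) or 22% (12:12 overall) chance. Averaged over allocation, type I error is 5%.

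**Price of the term when π = 0.** Under reading A, hypothesis 1 power falls from 72% to 71% at 6:6, 70% at 7:5, 66% at 8:4 and 59% at 9:3. The average is 67% under simple allocation and 69% if 12:12 overall. Average power breaks even at π of about 0.4 and 0.3 pulse respectively. Under reading B, power at 6:6 is 44% without period and 43% with it, and break-even under simple allocation is about 0.6 pulse.

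**The case against.** The strongest reply is that nothing shows an order effect. Both admissions use the same estradiol pretreatment, cycle timing, clock windows and ban on daytime sleep, and random order already protects validity on average. Below break-even the term lowers average power. Under reading B and simple allocation, break-even lies above the whole assumed range. Control data were complete by April 2017, so a new primary model could look post hoc.

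Most of this stands as a limit on weight. The effect size is assumed, and below break-even the only gain is freedom from conditional bias. It does not remove the point: the trial reports one realised split in groups of 12, and averaging over splits that did not occur does not help that estimate. Lateness is answered by dating the change and showing both results.

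Three stronger readings are tempting, and the documents do not support them:

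- A reader might infer that the planned test has an inflated type I error. Averaged over allocation it does not; the 7% for hypothesis 2 belongs to one unfavourable split at the top of the assumed range.
- A reader might infer that allocation was unblocked. Naming PROC PLAN without its settings shows only that blocking is not described.
- A reader might infer that actigraphy can settle the sleep route. Routine actigraphy is promised in an April 2017 update, when controls were already complete; before that, sleep was to be evaluated only when possible.

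**Conclusion.** The omission is real and runs through the primary, fallback, group-comparison and secondary models. If the night-to-day change depends on admission order, the progesterone estimate carries a bias of π(nA − nB)/12 in the realised split: 0.08 to 0.17 pulse at 8:4 for the assumed 0.25 to 0.5 pulse. At 6:6 the effect stays in the error. Over randomisation the bias is zero and type I error is about 5% or below.

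This is a worthwhile, cheap improvement. It is not an error in a stated figure and not evidence that the result is biased. The bias formula does not depend on how 1.24 is read; the power and break-even figures do. If 1.24 is a per-admission SD, the gain within the assumed range is mainly freedom from conditional bias, not power.

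**What to change.** Before the unblinded treatment comparison, add period and period by assessment time as fixed effects to the primary models and the count fallback; the secondary models then inherit them. The interaction is needed because the tested contrast is a change. In addition:

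- Code order as first versus any later admission. A woman whose first admission is replaced by a repeat then has two later admissions and adds nothing to the order contrast.
- Fit period within controls for hypothesis 1, which concerns "normally cycling adult women during the follicular phase". Use an order effect common to both groups only in the joint hypothesis 2 model.
- Report sequence counts by group, and the results with and without period.
- If control data are already unblinded (the progesterone assays disclose treatment), date the change and show both results side by side.
- Compare sleep on first and later nights only where actigraphy or other sleep data exist; they may be missing for controls.

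The cost is wording and 1 df, with no new data or visits. The hypothesis 1 price is shown in the working. For hypothesis 2 under reading A, the difference detectable with 80% power moves from 1.48 pulses to 1.49 when both groups have the same split, and to 1.58 at 8:4 against 4:8.
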